Subject allocation to procedure group will be via variable block randomization with varying block sizes of two, four and six used at random to minimize the likelihood of predicting the next procedure group assignment. In addition, randomization will be stratified by test site.

Randomization will be attained using computer generation sequence methodology, insuring that the randomization methodology and the generated allocation sequence is concealed from the investigator and subjects.

Concealment will be insured as follows:

- (ii) Each computer-generated randomization sequence is unique and will therefore not be able to be replicated.
- (iii) Randomization will occur to either 'Procedure Group A' or to 'Procedure Group B' rather than to a test or placebo group, and only the study Sponsor will know which assignment (A or B) corresponds to the active device and which corresponds to the fake device. The Sponsor will not reveal this information to any source (investigators, subjects, or study Monitor) until the final study data analysis is complete.

Once a subject has qualified for and been enrolled in the study, the Principal Investigator will contact the study Monitor who will act as the central source for providing sequential subject procedure group assignment.

SUBJECTS

Recruitment

Subjects will be recruited from among the Principal Investigator's/test site's pool of patients who are currently being treated for, or who are seeking treatment for, diagnosed minor episodic chronic low back pain of musculoskeletal origin, or from response to the following recruitment materials.

a) Flyer

WANTED

**ADULTS WITH LOW BACK PAIN ONGOING
OVER THE LAST 3 MONTHS FOR A
CLINICAL STUDY OF THE EFFECTS OF
LOW LEVEL LASER LIGHT ON
REDUCING LOW BACK PAIN**

**THIS STUDY INVOLVES EIGHT
LASER LIGHT PROCEDURES
WITH THE ERCHONIA® FX-635™ LASER
OVER 4 WEEKS AT THE TEST SITE.**

THERE ARE TWO MORE VISITS TO THE TEST SITE
ONE MONTH AND TWO MONTHS AFTER
THE LAST LASER LIGHT PROCEDURE.

COMPENSATION OF \$300
FOR QUALIFIED PARTICIPANTS

FOR MORE INFORMATION PLEASE CONTACT:

<PI name>
<test site name & location>
<phone # and/or e-mail>

b) Newspaper Ad

Low Back Pain Research Study

This study is to see if the Erchonia® FX-635™, a non-invasive, investigational device that uses low-level laser light, can help to relieve minor low back pain that has been ongoing for at least 3 months.

The study involves eleven visits to a test site and recording some information at home.

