Compensation up to \$300
For qualified participants

Please contact <PI name> at
<test site name & location> at
<phone and/or e-mail> for details.

Compensation

A subject who completes his or her participation in this clinical study through to the final post-procedure administration visit will receive financial compensation of \$300.

A subject will not be charged for the cost of the study procedures with the Erchonia® FX-635™ Laser or for the cost of any other directly-related evaluations or measurements that occur as part of his or her participation in the study.

Sample size

There will be 64 qualified subjects enrolled in this clinical study:

- 32 subjects in the active procedure group
- 32 subjects in the control procedure group

Rationale for sample size

In the determination of sample size, the following parameters have been established for the purposes of assessing efficacy of the Erchonia® FX-635™ in this clinical study:

- Individual subject success criteria defined as a 30% or greater reduction in self-reported Degree of Pain rating on the 0-100 VAS from baseline to study endpoint evaluation.
- Overall study success criteria defined as a minimum 35% difference between the test device group and the placebo device group in the proportion of individual successes.
- It is anticipated that about 55% of subjects in the test device group and about 20% of subjects in the placebo device group will meet the individual success criteria, and
- Intended application of a two-tailed test with an alpha value of 0.05 and Power of 0.8

The **clinical relevance** of a 30% change in VAS score and a 35% difference in the proportion of individual successes between procedure groups has been well previously established over the past 8 years by FDA's Division of Surgical, Orthopedic and Restorative Devices through numerous pre-IDE reviews, the results of said studies that were subsequently used to successfully support various pain-reduction related indications for various Erchonia Corporation light therapy devices under Product Code NHN for the 510(k)s as listed below:

1. **K101430**; 06/22/10: "The FX-635™-AC DermaScanner™ is indicated, while using the red diodes, for adjunctive use in providing temporary relief of minor chronic neck and shoulder pain of musculoskeletal origin."
2. **K100509**; 06/08/10: "The Erchonia THL1 is indicated for use in providing temporary relief of minor chronic neck and shoulder pain of musculoskeletal origin."

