- Oswestry Disability Index (ODI)/Oswestry Low Back Pain Questionnaire
- Range of Motion (ROM)
- Assessment Investigators' Adverse Events Evaluation

STUDY ENDPOINT EVALUATION: TWO MONTHS POST-PROCEDURE EVALUATION

- VAS Degree of Pain Rating
- Oswestry Disability Index (ODI)/Oswestry Low Back Pain Questionnaire
- Range of Motion (ROM)
- Subject Satisfaction With Study Outcome
- Subject Perceived Group Allocation and Rationale
- Assessment Investigator's Perceived Subject Group Allocation and Rationale
- Assessment Investigators' Adverse Events Evaluation

ADVERSE EVENTS

At each evaluation and procedure administration test site visit throughout the clinical study, and at any other time throughout the duration of the clinical trial that is necessary, any and all potential adverse events reported by a subject or observed by an investigator will be recorded on the case report form, and subsequently evaluated by a suitably qualified independent reviewer for determination of relationship to the study treatment and whether or not any corrective action needs to be taken. All potential adverse events recorded will be appropriately reported to the governing IRB, as applicable.

It is unlikely and not expected that any adverse events will result from implementation of this clinical study protocol. Prior clinical trials using low level laser light have not typically yielded any adverse events or reactions. However, potential adverse events that may feasibly occur from application of the Erchonia® FX-635™ include, but are not necessarily limited to: skin irritation, discoloring, rash, indentations and infection.

STATISTICAL ANALYSIS

PRIMARY EFFICACY OUTCOME MEASURE: CHANGE IN SUBJECT SELF-REPORTED VAS PAIN RATING FROM BASELINE TO STUDY ENDPOINT

Primary efficacy outcome measure for this clinical study will be a statistically significant difference in the proportion of subjects between test and control groups who achieve a clinically meaningful and statistically significant decrease in self-reported VAS pain rating from baseline to study endpoint.

Subjects meeting Individual Success Criteria

The individual subject success criteria is defined as a 30% or greater decrease in self-reported VAS pain rating at study endpoint relative to baseline.

Overall Study Success Criteria.

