- **Null Hypothesis:** There will be no statistically significant difference in the proportion of individual successes, as defined, between the test and control groups.
- **Alternative Hypothesis:** There will be a statistically significant difference in the proportion of individual successes, as defined, between the test and control groups, to the effect of 35% or greater.

PRIMARY EFFICACY OUTCOME STATISTICAL EVALUATION METHODS

- **Intent to Treat (ITT) Principle:** Primary efficacy analysis will be according to the intent to treat (ITT) principle; wherein subjects will be included in the analysis if they were randomized to study procedure group, had a valid baseline (pre-procedure) visit including the required low back pain VAS recording; and received at least the first study procedure administration.
- **Missing data** will be handled through Last Observation Carried Forward (LOCF): by carrying forward the last recorded observation to fill in the subsequent missing value.
- **Per-Protocol Analysis** will also be performed for the set of all subjects who were randomized to procedure group and completed the study according to the full protocol.
- **Primary analysis of efficacy** will be according to intent to treat (ITT) analysis through the application of:
 - 1) **Fisher's exact test** to compare the proportion of success between the test and the control groups, considering that randomization has been diligently conducted and important covariates between the two groups are well balanced.
 - 2) **Parametric ANCOVA model** analysis with the mean change from baseline to study endpoint in low back pain rating on the VAS as the dependent variable, procedure group as the independent variable of interest and baseline low back pain VAS rating as a covariate. A two-tailed significance level of 5% will be considered to be statistically significant.
- **Covariates:** The following potential covariate baseline variables will be adjusted, as applicable, through application of an ANCOVA analysis for the continuous variables and linear regression analysis for categorical variables.
 - ✓ Baseline Oswestry Disability Index (ODI) score
 - ✓ Age

SUPPORTIVE SECONDARY OUTCOME MEASURE: OSWESTRY DISABILITY INDEX (ODI) SCORE

ODI scores will be considered a secondary endpoint to support the primary pain evaluation outcome measure of subject self-reported degree of low back pain levels recorded on the 0-100 Visual Analog Scale (VAS).

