- (ii) The percentage of times the assessment investigators correctly perceived subjects' procedure group assignment and the percentage of times the assessment investigators did not correctly perceive subjects' procedure group assignment will be calculated.
- (iii) The **Fischer's Exact categorical analysis technique** for comparison of proportion of successes (accurate procedure group assignment determination) and failures (inaccurate procedure group assignment determination) between subject groups will be performed for each of the subject and assessment investigator determinations.
- (iv) **Qualitative analysis confirmation:** Evaluation of the comments provided by the subject and assessment investigators in the rationale section to explain the guess at group assignment will be evaluated and interpreted as follows to either support or negate the numerical findings:
 - *Positive blinding efficacy* will be supported through qualitative assessment of comments provided to support perceived group assignment that pertain to the determination being made based on treatment efficacy or lack thereof; e.g.: 'I can bend down and walk around more easily and with less pain than before, so I believe I got the real treatment' or 'I haven't noticed any change in my low back pain, so I believe I got the fake treatment.'
 - *Blinding will be determined to have failed* if comments provided to support perceived group assignment pertain to factors such as sensation/visual clues, such as 'I saw/didn't see a light go on', or other factors that pertain to blinding having been compromised such as 'I overheard the doctor saying I wasn't getting the real treatment.'

SAFETY ANALYSES

Safety analyses will be based on all subjects who were randomized to the test or to the placebo procedure group. Safety will be assessed by evaluating and comparing frequency and incidence of observed and/or reported adverse events between test and placebo procedure groups. A chi-square test with a continuity correction will be performed to compare the percentage of subjects who had adverse events between test and placebo group subjects.

Analysis of results will be performed by individual test site and pooled across test sites. Application of a balanced test-control group study design incorporating a varied block by test site randomization procedure will contribute to statistical justification of pooling data across the different test sites.

END OF DOCUMENT

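### The continuity-corrected chi-square test for adverse events is very conservative at the few events expected; Boschloo's exact test holds the 5% level and has more power (minor, inexpensive improvement)

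*Combined protocol and SAP*

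**What the plan says.** All citations are to the combined protocol and SAP.

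- Safety Analyses: "A chi-square test with a continuity correction will be performed to compare the percentage of subjects who had adverse events". The population is everyone randomized: "Safety analyses will be based on all subjects who were randomized to the test or to the placebo procedure group". The same section also plans a comparison of frequency and incidence between the groups. It gives no significance level, expected event rate or decision rule.
- Adverse Events: "It is unlikely and not expected that any adverse events will result from implementation of this clinical study protocol". Every potential event goes to an independent reviewer, who judges its relationship to treatment and whether action is needed.
- Sample size: "32 subjects in the active procedure group" and "32 subjects in the control procedure group".
- Primary Efficacy Outcome Statistical Evaluation Methods: Fisher's exact test is named "to compare the proportion of success between the test and the control groups". The level is given there, in the ANCOVA item: "A two-tailed significance level of 5% will be considered to be statistically significant". The Blinding Efficacy Evaluation also uses Fisher's test.
- Randomization: stratified by site, with "varying block sizes of two, four and six used at random", so a final split of exactly 32 and 32 is planned but not guaranteed.

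**The concern.** The continuity-corrected chi-square is a large-sample test with a built-in conservative adjustment. The plan applies it to what will probably be its sparsest binary comparison, while it uses an exact test for efficacy and for blinding. When few events occur, the corrected test runs far below its nominal level. A real excess in one arm can then be reported as not significant although another test that also respects the 5% level would flag it.

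In a safety comparison a missed excess is the more costly error. The results are meant to support a 510(k) submission, where a non-significant comparison could be read as reassurance.

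**Working it through.** **Arm size.** The plan states no sample size or power for the safety test, so its efficacy calculation is the only figure to reproduce. With 55% versus 20%, two-sided 5% and 80% power: n = [1.96·√(2·0.375·0.625) + 0.8416·√(0.55·0.45 + 0.20·0.80)]² / 0.35² = (1.3419 + 0.5373)² / 0.1225 = 28.8, so 29 per group. The plan's inflation, 29/0.917 = 31.62, gives 32. Both figures reproduce.

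**Expected counts.** With T events in total at 32 versus 32, the expected count per arm is T·32/64 = T/2. Five events give 2.5 per arm. The count stays below 5 for every T below 10, that is, for fewer than 10 of 64 subjects (15.6%) with an event.

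**Single tables at 32 versus 32.** The corrected statistic is N(|ad − bc| − N/2)² / (product of the four margins).

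- 5 versus 0: 64·(160 − 32)² / (32·32·5·59) = 1,048,576 / 302,080 = 3.47, p = 0.062. Fisher: 2·C(32,5)/C(64,5) = 2·201,376 / 7,624,512 = 0.053. Boschloo: 0.033.
- 7 versus 1: 64·(192 − 32)² / (32·32·8·56) = 1,638,400 / 458,752 = 3.57, p = 0.059. Fisher: 0.053. Boschloo: 0.033.

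Boschloo's test orders tables by the Fisher p-value. Its own p-value is the probability of a table at least that extreme, maximized over the unknown common event rate.

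**All tables at 32 versus 32 (33·33 = 1089), two-sided 5%.**

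- Corrected chi-square and Fisher agree in 1085. The four exceptions are 5 versus 13 and its mirror images, where the smallest expected count is 9. In the 110 tables with an expected count below 5, they never differ.
- In those 110 tables Boschloo rejects eight that the planned test does not: 5 versus 0, 7 versus 1, and their mirror images.
- Boschloo's maximum size over all common rates is about 4.7%, so the gain does not come from exceeding 5%.

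**Size and power at 32 versus 32.** All rates are assumptions, because the documents give none.

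| Rates | Corrected chi-square | Fisher | Boschloo |
|---|---|---|---|
| 5% vs 5% (size) | 0.2% | 0.2% | 0.85% |
| 5% vs 1% | 0.3% | 0.3% | 1.5% |
| 10% vs 1% | 7% | 7% | 16% |
| 15% vs 1% | 27.5% | 27.5% | 43.6% |
| 20% vs 5% | 27.6% | 27.6% | 36.7% |

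Hand check for 15% versus 1%: P(5 vs 0) = C(32,5)·0.15⁵·0.85²⁷·0.99³² = 0.138, and P(7 vs 1) = C(32,7)·0.15⁷·0.85²⁵·32·0.01·0.99³¹ = 0.023. Their sum, 0.161, is the whole gain from 27.5% to 43.6%.

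**Unequal arms, 31 and 33.** Power at 15% versus 1%:

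- Excess in the smaller arm: corrected chi-square 27%, Fisher 55%, Boschloo 58%.
- Excess in the larger arm: 30.0%, 30.1% and 46.5%. For 5/33 versus 0/31 the corrected test gives 0.073 and Fisher 0.053; neither rejects.

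**The case against.** **Fisher.** A reader might infer that any exact test, and in particular the plan's own Fisher test, would find more. At the planned 32 versus 32 it does not: in sparse tables its decisions are those of the corrected chi-square, and both are equally conservative. This part of the objection stands in full.

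**Unequal arms.** A reader might also point to 4/31 versus 0/33, where Fisher gives 0.0495 and the corrected test 0.106. That example is fragile. The one-tail probability is C(31,4)/C(64,4) = 31,465/635,376 = 0.0495. The opposite tail, C(33,4)/C(64,4) = 40,920/635,376 = 0.064, drops out of the two-sided p-value only because it is slightly more probable. Doubling the tail gives 0.099, close to the corrected test. Fisher's advantage at 31 and 33 appears mainly when the smaller arm has the excess.

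**Sample size.** If events are as rare as the plan expects, no test is informative with 32 per arm; at 5% versus 1% even Boschloo reaches only 1.5%. This stands. The larger gains require rates well above what the plan expects in the active arm.

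**Stakes.** Nothing in the plan turns on this p-value, and it has other safety routes: descriptive comparison of frequency and incidence, and independent review of each event. This also stands and sets the severity. It does not remove the point that a better test is available at the same level.

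**Conclusion.** The point holds as a minor improvement. With the few events the plan expects, the named test is very conservative. At 32 versus 32, Boschloo's test stays within 5% and rejects the two low-count patterns, 5 versus 0 and 7 versus 1, that the planned test leaves just above 0.05. The gain is about 9 percentage points of power at 10% versus 1% and at 20% versus 5%, about 16 points at 15% versus 1%, and about 1 point at 5% versus 1%.

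This rests on three assumptions: a two-sided 5% level carried over from efficacy, event rates that the documents do not give, and arms at or near 32 each.

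A reader might go further and conclude that the safety analysis is invalid. The documents do not support that. The planned test errs towards too few rejections, no safety conclusion is tied to it, and the low power comes chiefly from 32 subjects per arm and rare events.

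**What to change.** In Safety Analyses, replace the continuity-corrected chi-square test with a two-sided Boschloo exact test. Report the difference in adverse-event percentages between the groups with an exact 95% confidence interval. State the significance level there, since none is given. The interval matters as much as the test: it shows how large an excess the data cannot exclude when few events occur.

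The cost is a sentence or two of text, with no new data, visits or subjects. The downside is a less familiar test that differs from the Fisher test used for efficacy and blinding. Substituting Fisher would make the plan uniform, but it would change no sparse-table decision at 32 versus 32.
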